10.3.2 Analysis of Primary Endpoint

a) Imaging interpretation ^{68}Ga -PSMA-11 PET:

PET images will be interpreted by 3 different readers in a random order at separate reading sessions. Cross-sectional imaging from the PET will be available for anatomic correlate. Final reads for each patient will be interpreted as positive or negative for the presence of pelvic nodal disease, and positive or negative for the presence of osseous metastatic disease and soft tissue metastases outside of the pelvis.

Visual interpretation of PET data:

Regions of suspected disease will be graded on a two-point scale by each reader (0 = Negative or 1 = Positive). A region will be judged as positive if at least 1 lesion in this region is visually positive.

- i) Lymph nodes will be considered positive if the ^{68}Ga -PSMA-11 uptake is focal and greater than adjacent background. Pelvic lymph nodes will be subclassified according to their localization as follows: R/L obturator; R/L external iliac; R/L internal iliac; and other (total of 7 subgroups).
- ii) Visceral lesions will be considered positive if the ^{68}Ga -PSMA-11 uptake is focal and greater than physiologic background activity of the involvement organ or anatomic site.
- iii) Bone lesions will be considered positive if the ^{68}Ga -PSMA-11 uptake is focal and greater than physiologic bone marrow.
- b) Pathology analysis: Specimens from prostatectomy will be evaluated for the presence of nodal metastasis. This will be reported on a per-patient basis as positive or negative.
 - i) Nodes will be marked by location per site-specific protocol. For example if the urologist removed left and right nodal regions separately, then that patient will have two nodal regions (left/right). If a different surgeon removes nodes in six groups

(bilateral internal/external/obturator nodes), then that patient will have six nodal regions that will be analyzed.

- ii) Although not routinely performed during standard practice, immunohistochemical staining for PSMA-11 of tumor specimens (primary and lymph node metastases) may be performed, but is not required for this study.
- iii) The number of nodes counted on pathology will also be recorded.

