c) Analysis plan for Primary Aim 1: For this study to reach success, 2 out of the 3 readers will have to demonstrate a detection sensitivity of 65% or greater for nodal metastases. Additionally, 2 out of the 3 readers will have to demonstrate a detection specificity of 90% or greater for regional nodal metastases based upon region as defined below on a per patient level. The sensitivity, specificity, positive and negative predictive value of PSMA-11 PET for the detection on a per patient basis will be determined using the below criteria:

- i) True positive patient:
 - (1) PSMA-11 PET-positive for regional nodes; pathology at prostatectomy positive for regional nodes. Region will be defined by the granularity used by the urologist at time of prostatectomy. Sensitivity will be calculated at a patient level by region, meaning that one correct region would make a true positive on a patient level. Only one node needs to correspond between imaging and pathology for a patient to be considered a true positive.
 - (2) PSMA-11 PET-positive for regional nodes; pathology negative for regional nodes; imaging after prostatectomy demonstrates node was not removed at surgery; and follow-up biopsy or imaging demonstrates presence of nodal disease.
 - (a) Criteria for positive node on follow-up imaging: imaging within 3 to 12 months; the node decreases by more than 30% (for patients undergoing systemic treatment or focal therapy at this site); or increase by more than 20% in short axis diameter in the absence of treatment (with a minimum of 3 mm in change in size).
- ii) True negative patient:
 - (1) PSMA-11 PET-negative for regional nodes; pathology at prostatectomy negative for regional nodes.
- iii) False positive patient:
 - (1) PSMA-11 PET-positive for regional nodes; pathology at prostatectomy is negative; and imaging after prostatectomy demonstrates that node is no longer present.
 - (2) PSMA-11 PET positive for regional node, but pathology at prostatectomy is positive for node but in a different nodal region than that node seen on PSMA-11 PET.

iv) False negative patient:

- (1) PSMA-11 PET negative for regional nodes, but pathology at prostatectomy is positive.

v) Non-evaluable:

- (1) PSMA-11 PET positive for regional nodes; pathology negative for regional nodes; imaging after prostatectomy demonstrates node was not removed at surgery; and no definitive follow-up is available.

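### A node-positive patient whose PET uptake lies only in the wrong region is scored as a false positive, so his miss never enters primary sensitivity

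*Combined protocol and SAP*

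**What the plan says.** All of the following is in section 10.3.2 unless stated.

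- **Success rule (c).** Two of three readers must reach 65% sensitivity, and "2 out of the 3 readers will have to demonstrate a detection specificity of 90% or greater for regional nodal metastases". The text ties specificity to region, counted at patient level. Section 2.5 likewise sets the primary objective per patient with regional correlation.
- **True positive (1).** Matching is generous: "one correct region would make a true positive on a patient level".
- **False positive (2).** A PET-positive patient whose "pathology at prostatectomy is positive for node but in a different nodal region than that node seen on PSMA-11 PET".
- **False negative, the only rule.** "PSMA-11 PET negative for regional nodes, but pathology at prostatectomy is positive".
- **Pathology (b).** Nodal metastasis in the specimen: "This will be reported on a per-patient basis as positive or negative". Regions follow the surgeon's own grouping, with examples of two and of six.
- **PET-positive, pathology-negative patients.** There are three outcomes. True positive: "imaging after prostatectomy demonstrates node was not removed at surgery; and follow-up biopsy or imaging demonstrates presence of nodal disease". False positive: "pathology at prostatectomy is negative; and imaging after prostatectomy demonstrates that node is no longer present". Non-evaluable: "imaging after prostatectomy demonstrates node was not removed at surgery; and no definitive follow-up is available".

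No formula for sensitivity or specificity is printed; the plan says only that the listed categories determine them. Section 10.3.3 (secondary endpoints) calls a negative biopsy of the correct node a false positive and makes false positive the default for nodes that meet no other criterion. Section 10.3.2 does not refer to it.

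**The concern.** Sensitivity asks what share of patients with nodal disease PET finds. A patient with proven nodal metastasis whose uptake lies only in non-matching regions has disease that PET did not find where it was. The plan's own pathology rule calls him positive, yet he can never be a false negative.

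Three consequences follow under the standard formulas:

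- A reader who sees nothing in this patient is charged with a miss. A reader who marks the wrong region is not.
- Whether the patient belongs to the diseased group depends on the reader, so the three readers can have different sensitivity denominators for the same pathology. It also depends on how finely the surgeon grouped the nodes: the same scan and the same disease could be a match with two regions and a mismatch with six.
- He enters the specificity denominator as a failure, although he has nodal disease.

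Both quantities feed the trial's only success rule. A reader can meet the 65% cut-off because PET pointed to the wrong place, or miss the 90% cut-off because of patients who are node-positive.

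A smaller gap sits beside this. Follow-up of a retained node can make a patient a true positive or non-evaluable, but never a false positive. A definitive negative result, such as a negative biopsy of that node, has no category in the primary rules.

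**Working it through.** **Inputs from section 10.2.1.** 200 enrolled; 25% without prostatectomy; 30% node-positive; PET sensitivity 65% against 45% for conventional imaging; power 80%, significance level 0.01. The plan's 61 reproduces as a one-sided, one-sample calculation:

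[2.326 × √(0.45 × 0.55) + 0.842 × √(0.65 × 0.35)]² / 0.20² = 60.7, so 61.

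The plan's rates give a different count: 200 × 0.75 = 150 operated, 150 × 0.30 = 45 pathology-positive and 105 pathology-negative. That shortfall is a separate matter; 45 and 105 are used here.

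**Assumption.** The number of mislocalised patients, k, is not in the documents.

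**Formulas**, with no retained-node or non-evaluable patients:

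- As written: Se = TP/(45 − k), Sp = TN/(105 + k).
- By pathology status: Se = TP/45, Sp = TN/105.

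For any k above zero, with TP and TN above zero, the rule raises sensitivity and lowers specificity.

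**Four mislocalised patients** (TP 27, PET-negative FN 14, TN 99, pathology-negative FP 6):

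| | As written | By pathology status |
|---|---|---|
| Sensitivity | 27/41 = 65.9% | 27/45 = 60.0% |
| Specificity | 99/109 = 90.8% | 99/105 = 94.3% |

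Defined by PET result, PPV is 27/(27 + 6 + 4) = 27/37 = 73.0% and NPV is 99/(99 + 14) = 99/113 = 87.6%, the same as now. Merely relabelling the four as false negatives in one 2×2 table would change these to 27/33 = 81.8% and 99/117 = 84.6%.

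**One mislocalised patient**, examples chosen at the cut-offs:

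- By pathology status 30/45 = 66.7% and 95/105 = 90.5% (pass); as written 30/44 = 68.2% and 95/106 = 89.6% (fail).
- By pathology status 29/45 = 64.4% and 96/105 = 91.4% (fail); as written 29/44 = 65.9% and 96/106 = 90.6% (pass).

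**Simulation.** One reader, 1,000,000 trials, 45 and 105 fixed, comparing the joint verdict under the two countings at mislocalisation rates of 2%, 5% and 10% of pathology-positive patients:

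| Setting | Verdict differs | Pass probability, by status → as written |
|---|---|---|
| 65% is sensitivity under the plan's rules (correct localisation 0.65 × (1 − rate)); Sp 92% | 9%, 16%, 15% | 32→34%, 24→26%, 13→15% |
| 65% is the correctly localised fraction; Sp 92% | 10%, 20%, 29% | 37→39%, 37→36%, 37→24% |
| 80% correctly localised; Sp 97% | 1%, 2%, 9% | 99→99%, 99→98%, 99→91% |

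In the second setting the chance of meeting the sensitivity cut-off alone goes from 48% to 58%, 70% and 85%, and the specificity cut-off alone from 78% to 67%, 51% and 28%. The opposing shifts partly cancel in the joint verdict. With three independent readers of equal accuracy and the 2-of-3 rule, the second-setting verdict differs in 16%, 30% and 37%; with identical readers the one-reader figures apply.

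**Retained node, one patient with a negative biopsy.** 94/105 = 89.5% if he counts as a false positive; 94/104 = 90.4% if he has no category and is left out.

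**The case against.** The strongest reply is that region matching is deliberate. Section 2.5 announces it, and 10.3.2 c) attaches the specificity criterion to region at patient level. A PET call in the wrong region is an error, and the authors chose to charge it to specificity. This stands as far as specificity goes. A reader might infer that the specificity treatment is a slip to be deleted; the documents do not support that, because it is a stated choice. What the reply does not explain is why the same patient escapes the sensitivity count. Matching means that wrong-region uptake is not a detection. It does not make a node-positive patient disease-free.

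The size is also open to challenge. At a 10% rate with 65% correctly localised, 10 of every 75 PET-positive, node-positive patients (13%) would have no matching region, although one match is enough. Where nodes are grouped only as left and right, that means uptake solely on the wrong side. Nothing in the documents supports such a rate, and the larger figures come from settings close to the cut-offs. This stands, and it limits what can be said about impact.

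On the retained node, 10.3.3 reports over all imaged regions, covers patients undergoing nodal dissection and already contains the false-positive answer. A reader might infer that the plan has no answer anywhere; it has one, but the primary section does not point to it. Stable imaging can also be read as lacking definitive follow-up, which leaves chiefly the negative biopsy.

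**Conclusion.** The classification is wrong as written for sensitivity. The conclusion rests on the standard formulas, which the plan does not print, and on the literal rules, which leave no other category for this patient. Confidence in that logic is high.

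The size is uncertain, because the mislocalisation rate and the specificity are assumed. Depending on the setting, one reader's verdict differs in 1% to 29% of simulated trials. If the plan's 65% is sensitivity under its own rules, the net pass probability moves by less than three percentage points, although individual verdicts change more often.

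Two stronger readings do not follow. A reader might conclude that the rule tilts the trial towards success; it raises sensitivity but lowers specificity, and the net direction is not fixed. A reader might also think that patients with both a matching and a non-matching region are left ambiguous; the one-correct-region rule makes them true positives.

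The retained-node gap is real but small: a missing cross-reference that can matter for a reader near 90%. The point as a whole should be fixed, since the remedy is cheap and the rule feeds the success criterion.

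**What to change.** Amend 10.3.2 c) as follows:

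1. Print the formulas. Count every pathology-positive patient with no matching region as a miss in patient-level sensitivity, and keep the one-correct-region rule.
2. State beforehand which specificity count decides the 90% criterion, and report specificity both with and without these patients. If they stay in, each one counts against both criteria, so passing can only become harder than under the present rules.
3. Keep PPV and NPV defined by PET result, and say that the four measures then do not come from a single 2×2 table.
4. Report the number of mislocalised patients for each reader.
5. For retained PET-positive nodes, cross-refer to the whole lymph-node classification in 10.3.3, its true-positive rules (including the PSA-response rule) as well as its false-positive rules. Define what counts as definitive follow-up and keep non-evaluable for patients without it. Report their number, with a sensitivity analysis that counts them all as false positives and then all as true positives.

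The cost is a wording change, submitted to the IRB as a protocol modification under section 9.1, and a little extra analysis of data already collected. Reported sensitivity will be lower if any patient is mislocalised, and specificity may fall slightly from the retained-node rule. Make the change before reads are linked to pathology; if they are already linked, report both countings.

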10.3.3 Analysis of Secondary Endpoints

We will report the sensitivity, specificity, positive and negative predictive value of PSMA-11 PET over all imaged regions as well as broken down by the following regions: extra-pelvic nodal metastases, visceral metastases and osseous metastases. Follow-up for extra-pelvic nodal metastases, visceral metastases and osseous metastases are defined as below:

i) Lymph nodes will be assessed by change in size. ^{68}Ga -PSMA-11 positive lymph nodes will be considered:

(1) True positive:

- If on follow-up imaging within 3 to 12 months, lymph nodes seen on CT or MRI decrease by more than 30% (for patients undergoing systemic treatment of focal therapy at this site) or increase by more than 20% in short axis diameter (with a minimum of 3 mm in change in size).

- If patients with solitary lymph node regions show a decrease of PSA by greater than 50% after targeted treatment (ie, external beam radiation) and the lymph nodes do not change in size (less than 30% decrease or less than 20% increase in short axis diameter).

(2) False positive:

- If on follow-up imaging within 3 to 12 months, sites of initial ^{68}Ga -PSMA-11 positive lymph node lesions seen on CT or MRI decrease by more than 30% without systemic therapy or focal therapy at this site.

- If ^{68}Ga -PSMA-11 positive lymph node lesions do not meet the criteria for above false positive or true positive findings.

ii) Visceral lesions (non-lymph node soft tissue or organ) will be assessed by change in size. ^{68}Ga -PSMA-11 positive visceral lesions will be considered:

(1) True positive:

- If on follow-up imaging within 3 to 12 months, visceral lesions seen on CT or MRI decrease by 30% (for patients undergoing systemic treatment of focal therapy at this site) or increase by 20% in largest diameter.

- If patients with solitary visceral metastasis show a decrease of PSA by greater than 50% after targeted treatment (ie, external beam radiation) and lesions do not change in size (less than 30% decrease or 20% increase in largest diameter).

(2) False positive:

- If on follow-up imaging within 3 to 12 months, sites of initial ⁶⁸Ga-PSMA-11 positive visceral lesions seen on CT or MRI decrease by more than 30% without systemic therapy or focal therapy at this site.

- If ⁶⁸Ga-PSMA-11 positive visceral lesions do not meet the criteria for above false positive or true positive findings.

iii) ⁶⁸Ga-PSMA-11 positive bone lesions will be considered:

(1) True positive:

- If there was a corresponding positive sclerotic lesion on the CT portion of the ⁶⁸Ga-PSMA-11 PET.

- If there is focal uptake seen on the baseline bone scan performed within one month of ⁶⁸Ga-PSMA-11 PET.

- If there is a lesion noted on the initial MRI performed within one month of ⁶⁸Ga-PSMA-11 PET.

- If within 12 months, follow-up CT demonstrates development of sclerosis.

- If within 12 months, follow-up MRI demonstrates a new bone lesion.

- If within 12 months, follow-up bone scan demonstrates new focal uptake.

(2) False positive:

- If ⁶⁸Ga-PSMA-11 positive bone lesions do not meet the criteria for true positive findings.

iv) Histopathology correlation: for lesions that have biopsy correlation, we will use the following criteria to determine positive and negative lesions:

(1) Positive HP/Biopsy: Confirmed sites of metastatic or tumor involvement by histopathology/biopsy will be discussed with the responsible physician/surgeon.

(2) Negative Biopsy: Patients with suspected tumor recurrence on ⁶⁸Ga-PSMA-11 PET with negative histopathology/biopsy will be handled as outlined below:

(a) Lymph nodes:

- For patients undergoing nodal dissection: Patients will be rescanned with dedicated CT or MRI to determine if the suspicious ⁶⁸Ga-PSMA-11-positive node was removed.

- If ⁶⁸Ga-PSMA-11 positive lymph node is still present, a repeat biopsy can be pursued if clinically feasible and applicable, or follow-up using imaging as described above will be performed.

- If the corresponding node was removed, then this will be considered a False Positive.
- For patients undergoing needle biopsy: Images of the procedure will be reviewed to determine if the correct node was biopsied.
 - If the correct node was biopsied, then a negative biopsy will be considered a False Positive.
 - If the incorrect node was biopsied, then follow-up imaging as described above will be performed.

(b) Bone lesions: Given the high rate of false negative biopsies for osseous metastases in patients with prostate cancer, patients with negative bone biopsies of ^{68}Ga -PSMA-11 PET-positive lesions will be further evaluated:

- If pathology demonstrates an alternative diagnoses that is known to be ^{68}Ga -PSMA-11-positive (eg, renal cell carcinoma (RCC) metastases; Paget's disease), then this will be considered a False Positive.
- If pathology is indeterminate, then follow-up imaging as described above will be performed to determine if the lesion is a True Positive or False Positive.

(c) Additionally a repeat ^{68}Ga -PSMA-11 can also be obtained, as allowable, in addition to repeat conventional imaging (CT and/or MRI) in cases of negative biopsy to determine if the biopsy was true negative or false negative.

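### Section 10.3.3 promises sensitivity, specificity and NPV for distant disease but classifies only PET-positive findings, and its catch-all false-positive bullets leave no non-evaluable class for lesions without follow-up

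*Combined protocol and SAP*

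**What the plan says.** Section 10.3.3 opens with the commitment "We will report the sensitivity, specificity, positive and negative predictive value of PSMA-11 PET over all imaged regions" and adds separate results for extra-pelvic nodal, visceral and osseous metastases. The synopsis and section 2.5 list the same four measures as the secondary objective, with biopsy and imaging follow-up as the comparator.

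The rules that follow in 10.3.3 cover PSMA-positive nodes, visceral lesions and bone lesions. Each list has two outcomes, true positive and false positive, and each has a residual false-positive category:

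- nodes: "positive lymph node lesions do not meet the criteria for above false positive or true positive findings"
- viscera: "positive visceral lesions do not meet the criteria for above false positive or true positive findings"
- bone: "positive bone lesions do not meet the criteria for true positive findings"

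The biopsy rules in 10.3.3 iv deal with findings suspected on PET. The only mention of true or false negatives in 10.3.3 is about the biopsy: a repeat scan may be obtained "in cases of negative biopsy to determine if the biopsy was true negative or false negative".

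For regional nodes, section 10.3.2 c is complete. A true negative is "PSMA-11 PET-negative for regional nodes; pathology at prostatectomy negative for regional nodes". A false negative is "PSMA-11 PET negative for regional nodes, but pathology at prostatectomy is positive". There is also a non-evaluable class for a PET-positive patient with negative pathology when "imaging after prostatectomy demonstrates node was not removed at surgery; and no definitive follow-up is available".

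**The concern.** Sensitivity needs false negatives, specificity needs true negatives, and NPV needs both. At distant sites the plan defines neither cell. An analyst who follows 10.3.3 to the letter can fill in only the PET-positive row of the table and must improvise the other. The easiest improvisation, treating every PET-negative man as free of distant disease, produces perfect sensitivity and NPV that the study never tested. Counting only the missed disease that happens to come to light gives a sensitivity that is too high.

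The residual false-positive bullets raise a separate problem. As worded, they do not distinguish a lesion that was imaged again and met no criterion from one that was never imaged again. Missing follow-up then counts as evidence against PET, whereas 10.3.2 sets the comparable regional case aside.

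**Working it through.** **Which cells are defined.** The documents state no sample size, power or precision for the secondary endpoint, so there is no figure of the plan's own to reproduce. The check is structural.

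| Measure | Formula | Cells defined for distant sites? |
|---|---|---|
| PPV | TP/(TP+FP) | both |
| Sensitivity | TP/(TP+FN) | FN missing |
| Specificity | TN/(TN+FP) | TN missing |
| NPV | TN/(TN+FN) | both missing |

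**Whether another section fills the gap.**

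- Section 5.3, under clinical follow-up, sends men with no PET-positive disease to prostatectomy. Item b starts distant work-up only after a positive PET.
- Section 3.1 requires a diagnostic CT or MRI within 90 days of the PET, but no section names it as the reference for PET-negative men.
- Section 2.5 lists one-year PSA progression-free survival as a separate exploratory objective, not as a distant reference.
- Section 10.3.4 ties its sensitivity, specificity and NPV to histopathology or biopsy, and adds imaging follow-up only for PPV.

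None of these gives a PET-negative man a distant disease status.

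**How much the missing cells could matter.** The counts here are assumed: N = 200 scanned (the planned enrolment), one lesion per man, P men PET-positive, PPV 80%, and a fraction m of PET-negative men with missed disease. Then TP = 0.8P, FP = 0.2P, FN = m(200 − P) and TN = (200 − P) − FN.

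For P = 20: TP = 16, FP = 4, and 180 men are PET-negative.

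- m = 0: sensitivity 16/16 = 100%
- m = 2%: 16/(16 + 3.6) = 82%
- m = 5%: 16/(16 + 9) = 64%
- m = 10%: 16/(16 + 18) = 47%

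| P | Sensitivity at m = 0, 2, 5, 10% | Specificity, m = 0 to 10% |
|---|---|---|
| 10 | 100, 68, 46, 30% | 99.0 to 98.8% |
| 20 | 100, 82, 64, 47% | 97.8 to 97.6% |
| 40 | 100, 91, 80, 67% | 95.2 to 94.7% |

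NPV = 1 − m, that is 100, 98, 95 and 90% in every row. Specificity hardly moves.

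**Partial capture of false negatives.** Let true sensitivity be 65% (assumed) and let a fraction v of the false negatives come to light. Apparent sensitivity = 0.65/(0.65 + 0.35v): 100% at v = 0, 88% at v = 25%, 79% at v = 50%, and 65% only at v = 100%.

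**Catch-all bullets and PPV.** Assume 20 PET-positive lesions, u of them unverified, and 80% true among the verified. The catch-all reports 0.8(20 − u)/20. The upper bound, with all unverified lesions true, is [0.8(20 − u) + u]/20.

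- u = 5: 12/20 = 60% to 17/20 = 85%; among the verified 12/15 = 80% (Wilson 95% CI 54.8 to 93.0%)
- u = 10: 8/20 = 40% to 18/20 = 90%; among the verified 8/10 = 80% (Wilson 95% CI 49.0 to 94.3%)

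The catch-all always reports the lower bound. The 80% among the verified carries over to all lesions only if the unverified ones resemble them.

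**The case against.** **Already planned.** Section 10.3.4 commits to PPV per patient and per region with two-sided 95% confidence intervals, and the synopsis and section 2.5 list the incidence of osseous and distant lesions. This stands: much of the reporting exists, and what remains is mainly to withdraw the measures that lack a reference.

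**Another reading of the catch-all.** The rules in 10.3.3 are introduced as definitions of follow-up, so the residual bullets may be meant for lesions that were followed and stayed stable. Section 5.3 b also says that further imaging or biopsy will be done for PET-positive distant lesions. That reading is possible, and calling a stable, followed lesion false positive is a legitimate choice. The bullets do not say so, however, and 10.3.2 shows that the plan separates the two cases when it intends to.

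**Assumed sizes.** The 10% miss rate is high: with P = 20 it means distant disease in (16 + 18)/200 = 17% of men. Section 2.1 calls bone metastases rare at initial staging. The unverified shares of 25% and 50% have no support in the documents either. The figures show how the measures respond and are not forecasts.

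**Readings that go too far.**

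- A reader might infer that the trial will report 100% sensitivity. No section says that PET-negative men count as disease-free; the plan is silent.
- A reader might infer that PPV is biased downward overall. The catch-all alone lowers it, but other rules may raise it. For example, any bone lesion noted on MRI within one month counts as true positive. The net direction is unknown.
- A reader might infer from section 10.2.1 that men without prostatectomy are left out of the secondary analysis. That sentence is one of the assumptions behind the primary-aim sample size. Section 10.3.1 and item v (2) of 10.3.2 c both limit the exclusion to the primary analysis. Only the remark on central review needs clarifying.
- The missing follow-up imaging row in the study calendar proves nothing about PET-negative men, because the planned follow-up of PET-positive men is not shown there either.

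**Conclusion.** The point holds for distant disease. Of the four measures promised in 10.3.3, only PPV is identified by the rules given. Sensitivity and NPV are undefined, or 100% by construction if PET-negative men are presumed disease-free, and sensitivity is inflated if false negatives are only partly found. Specificity is formally undefined too, but changes little if missed disease is rare. I am confident in this part, because it follows from the text alone.

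The catch-all part rests on a literal reading of three bullets. On that reading, missing follow-up lowers PPV and contradicts the way 10.3.2 handles a regional node without definitive follow-up.

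The size of either effect cannot be stated, since the documents give no counts of distant lesions, missed disease or missing follow-up. Regional nodes have a full reference in 10.3.2, so the gap does not reach them, and the primary success criterion is not affected.

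**What to change.** 1. **Measures.** For extra-pelvic nodal, visceral and osseous disease, make the PPV with 95% confidence interval already planned in 10.3.4 the reported secondary measure, together with the PET detection rate and its 95% confidence interval. Drop sensitivity and NPV for these sites in the synopsis, section 2.5 and section 10.3.3. If they are kept, prespecify one reference and one follow-up window applied alike to all PET-negative men. Do not rely on those who happen to be followed: that lowers apparent NPV and can inflate sensitivity. If specificity is kept, label it as assuming that PET-negative men are free of distant disease.
2. **Catch-all bullets.** Reword all three. A PET-positive lesion not already classified by histology, baseline imaging or another listed criterion is false positive if it was imaged within the follow-up window that 10.3.3 already gives for that lesion type, and non-evaluable if it was not. Report the number non-evaluable, with PPV bounds counting them all as false positive and all as true positive.
3. **Clarification only.** State that the exclusion and no-central-review sentence in 10.2.1 applies to the primary aim, so that men with PET-positive distant disease who do not have surgery stay in the secondary PPV.

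Cost: wording changes, with no new visits or imaging. Sensitivity and NPV for distant disease are given up. If men without surgery are read centrally, the plan's own 25% of 200 means about 50 further scans, or up to 50 × 3 = 150 reads of images already acquired.
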